### 4.3 Recruitment

Potential patients for this study will be recruited by approximately 60 oncological centres in Europe, North America, South Africa and Australia specialised in endocrine oncology (endocrinology, gastroenterology, nuclear medicine), and with local access to or own experience in PRRT. Study sites will be interdisciplinary, consisting of an endocrine oncology sub-site, and a nuclear medicine sub-site. Study visits will be typically conducted at the recruiting sub-site, or as institutionally appropriate. Treatment visits for patients randomised to  $^{177}\text{Lu}$ -edotreotide will be performed in the collaborating nuclear medicine sub-site. Patients will be invited for study participation by the investigators in the context of specialised NET clinics. Interested patients will be provided with an information sheet and will undergo a detailed informed consent procedure prior to any study procedures (see Section 13.2). Recruitment will be continued until a sufficient number of patients has received at least one dose of PRRT treatment, or a sufficient number of events has been reached.

### 4.4 Withdrawal of Patients from Study Participation or Medication

#### 4.4.1 Withdrawal

Patients may decide to withdraw from the study at any time for any reason without prejudice to their further medical care. The investigator may withdraw a patient for any of the following reasons:

- Adverse event: if patient is unwilling to continue because of an AE or if continued participation of the patient would be an unnecessary risk to the patient's health, in the opinion of the investigator.
- Non-compliance
- Protocol deviation
- Pregnancy
- Lost to follow-up

A female patient who becomes pregnant during the treatment phase of the study must be discontinued from study treatment. See Section 8.3.1.1 for follow-up procedures in the case of pregnancy.

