#### 4.4.2 Withdrawal Procedures

Although patients are not obliged to give their reason(s) for withdrawing prematurely from a trial, the investigator should make every effort to ascertain the reason(s) for withdrawal while fully respecting the patient's rights. The investigator will make every effort to contact the patient and complete the EOS page on the case report form (CRF) and if possible the assessments outlined on EOS visit.

An EOS CRF page is to be completed for every patient, whether or not the patient completed the study. The reason for any early discontinuation should be indicated on this form. The primary reason for a patient withdrawing prematurely should be selected from the following standard categories of early termination:

- *Safety Reason/Adverse Event:* Clinical or laboratory events occurred that in the medical judgment of the investigator, for the best interest of the patient, are grounds for discontinuation. This includes serious and non-serious AEs regardless of relation to study medication. Criteria for dose-limiting toxicity are discussed in Section 5.4.3 and Table 9.
- *Protocol Violation:* The patient's findings or conduct failed to meet the protocol entry criteria or failed to adhere to the protocol requirements (e.g., drug non-compliance, failure to return for defined number of visits) as judged by the investigator or sponsor. The violation necessitated premature termination from the study.
- *Withdrawal of Consent:* The patient desired to withdraw from further participation in the study in the absence of an investigator-determined medical need to withdraw. If the patient gave a reason for withdrawing, it should be recorded.
- *Lost to Follow-Up:* The patient stopped coming for visits, and study personnel were unable to contact the patient (two unsuccessful phone contacts followed by registered letter and documentation in the source documents).

The date of study drug administration must be documented.

Appropriate follow-up of withdrawn patients will be performed, as required.

Attempts to contact a patient who withdraws from the study or is lost to follow-up must be documented.

Stopping rules for the entire study are described in Section 11.

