## 5.7 Treatment Compliance

A record of the number of  $^{177}\text{Lu}$ -edotreotide doses and everolimus tablets dispensed to and taken by each subject must be maintained and reconciled with study treatment and compliance records. Details of each study drug administration will be recorded in appropriate source documents and then reported in the CRF.

- $^{177}\text{Lu}$ -edotreotide:

$^{177}\text{Lu}$ -edotreotide will be administered by study personnel at the trial site only. In any case of interruption of  $^{177}\text{Lu}$ -edotreotide infusion, the infused and discarded amounts will be recorded.  $^{177}\text{Lu}$ -edotreotide is to be ordered on the day of randomisation. The first dose of  $^{177}\text{Lu}$ -edotreotide should be administered within 21 days of randomisation. In case of any delay, the site should check with the Sponsor via the site monitor and the reason for delay should be documented accordingly.

- Everolimus:

Subjects will be asked to maintain a dosing diary to record their daily administration of everolimus. At each visit, the subject should return the dosing diary. An evaluation of subject compliance with study treatments taken will be performed. The investigator will make every effort to bring non-compliant subjects into compliance. Compliance with dosing will be assessed through querying the subject during site visits and will be documented in the source documents and in the CRF, including treatment start and stop dates, dates for treatment delays and/or dose reductions.

The following deviations are defined as major protocol deviations, leading to exclusion from the PP set (see Section 9.3.3):

- $^{177}\text{Lu}$ -edotreotide arm:

- Subjects with incomplete  $^{177}\text{Lu}$ -edotreotide infusion, in which less than 50% of the total pre-scribed activity (GBq) based on initially dosimetry assessment was injected.
- Subjects in whom a dose was administered more than 30 days outside the per protocol date.

- Everolimus arm:
  - Subjects missing more than 14 doses, within a visit interval of 30 days (with exception of treatment interruptions due to toxicity, see Section 5.4.3.1).

Regardless whether a patient is compliant or non-compliant, the investigator must make every effort to perform all investigations according to the protocol for the entire duration of study participation.

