### 11.1.2 Stopping Criteria for Individual Patients

Study participation for an individual patient *must* be stopped

- In case of tumour progression (see Section 8.2.4)
- In case of excessive toxicity defined as an AE considered by the Investigator to necessitate permanent discontinuation of  $^{177}\text{Lu}$ -edotreotide, e.g., serious, treatment-related adverse events (see Section 8.3.2.5)
- If the patient decides to withdraw from the trial (see Section 13.2)

Study participation for an individual patient *may* be discontinued (see Section 4.4.1):

- For medical reasons at the discretion of the Investigator
- Due to non-compliance
- Following a protocol deviation
- Due to pregnancy
- If the patient is lost to follow-up.

Study treatment for an individual patient *must* be discontinued in the case of pregnancy (see Section 4.4.1). See Section 8.3.1.1 for follow-up procedures in the case of pregnancy.

Lu-edotreotide treatment for an individual patient *must* be discontinued in the case of hypersensitivity or anaphylactic reaction, or TLS or CRS development (see Section 8.3.2.4).

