3.4 Study Variables

3.4.1 Primary Variable

Progression-free survival

Progression-free survival will be determined starting from randomisation until the date of an event (PD or death). For the primary analysis, any withdrawal (or drop-out) before EOS visit at month 30 will be censored. Patients who have not shown progression at the end of the study (30 months) will also be censored.

In more details, the following rules will be applied for the main PFS analysis:

ITM-LET-01	Statistical Analysis Plan
------------	---------------------------

Table 1: PFS analysis rules

Situation	Date of Progression or Censoring	Outcome
Tumour progression or death	Earliest date of PD or death	Event (PD or Death)
No tumour progression and not death	Date of last adequate* radiological assessment	Censored
Unless:		
No baseline radiological tumour assessment	Date of randomisation	Censored
No adequate post-baseline radiological assessment and date of death, if any, is after 2 or more scan intervals following randomization**	Date of randomisation	Censored
New anticancer treatment started prior to tumour progression or death (whichever is earlier)	Date of the last adequate radiological assessment prior to start of new anticancer treatment or date of randomization (whichever is later)	Censored
Tumour progression or death documented immediately after 2 or more consecutive missing scan** following last adequate radiological tumour assessment or randomization (whichever is later).	Date of last adequate radiological tumour assessment or date of randomisation (whichever is later).	Censored

Table footnotes:

**Adequate radiological tumour assessment refers to an assessment with one of the following responses: CR, PR, SD, or PD.*

***The interval is higher than 2 times the maximal protocol scheduled RECIST 1.1 assessment interval (i.e. >222 days = 2*(90+21))*

For primary endpoint (PFS) main analysis, post-randomisation tumour assessment based on blinded central review compare to baseline will be used.

Where appropriate, sensitivity analyses will explore the impact of the chosen approaches and data issues observed during the blind review on the study results. These could include but not limit to:

- Blinded central RECIST 1.1 evaluation (main analysis) vs. Local RECIST assessments
- Applied main PFS censoring rules (main analysis, see Table above) vs. different approaches (e.g. next scheduled assessment date instead of date of radiological

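### Letting investigators end study participation for non-compliance or a protocol deviation stops centrally read imaging and may censor PFS informatively, possibly unequally by arm

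*Protocol*

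**What the plan says.** Three protocol sections let participation end for these reasons.

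- Section 4.4.1: "The investigator may withdraw a patient for any of the following reasons". The list includes non-compliance and protocol deviation, with no threshold and no arm named.
- Section 4.4.2 has an early-termination category, judged by the investigator or sponsor, which covers a patient who "failed to adhere to the protocol requirements (e.g., drug non-compliance, failure to return for defined number of visits").
- Section 11.1.2 lists "Due to non-compliance" and "Following a protocol deviation" as grounds on which study participation may be discontinued. These grounds are discretionary.

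Section 5.7 sets a follow-up duty: "Regardless whether a patient is compliant or non-compliant, the investigator must make every effort to perform all investigations according to the protocol". The sentence closes with "for the entire duration of study participation".

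For the primary endpoint, SAP 3.4.1 states that "any withdrawal (or drop-out) before EOS visit at month 30 will be censored". Protocol 9.2.1 has the same rule, and Protocol 9.3.3.1 and SAP 5.2.1 put the censoring date at the last adequate tumour assessment before withdrawal. The main PFS analysis uses blinded central reads (SAP 2.2.1). Progression after end of study is collected as local data (SAP 3.1), through six-monthly contacts (Protocol 7.4.1).

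**The concern.** Stopping a drug and leaving a study are different events, and these sections merge them. Once participation ends, the 5.7 duty ends too, because it lasts only as long as participation. One discretionary decision, made with knowledge of the treatment, can therefore switch off the imaging that supplies the primary endpoint.

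The patients affected are unlikely to be a random sample. Non-compliance may go with doing badly or with doing well, and either makes the censoring informative.

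The two arms also differ in how non-compliance can arise. 177Lu-edotreotide "will be administered by study personnel at the trial site only", at most four times. Everolimus is taken daily by the patient and recorded in a diary until progression. More drug non-compliance among controls is therefore plausible. If so, the censoring would be unequal between arms, and the comparison would no longer rest fully on randomisation.

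**Working it through.** **Path from the rule to the endpoint**

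1. The investigator ends participation for non-compliance or a deviation (Protocol 4.4.1, 4.4.2, 11.1.2).
2. The early-withdrawal visit falls within 28 days and follows the end-of-study list, which includes MRI/CT (Protocol 7.3.10, 7.3.11; Tables 1 and 2, footnotes U and ZZ). If the visit cannot be completed, 7.3.11 insists only on safety items, and MRI/CT is not among them.
3. The three-monthly imaging then stops. PFS is censored at the last adequate scan.
4. Later local progression does not enter the centrally read main analysis.

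**The plan's own figure**

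SAP 4 gives 180 events for 80% power at HR 11/17 = 0.647, 2:1 allocation, two-sided 5%. Schoenfeld's formula gives power = Φ(|ln 0.647| × √(180 × 1/3 × 2/3) − 1.96) = Φ(0.435 × 6.325 − 1.96) = Φ(0.79) = 78.6%. A Lakatos calculation (24 months of accrual, 48 months in total) needs 177 events for 80%. The plan's figure is reproduced, and this point does not dispute it. With 180 events the standard error of log HR is 1/√(180 × 2/9) = 1/√40 = 0.158.

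**Possible size of the effect**

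The documents give no withdrawal rate for non-compliance, so every rate here is an assumption. The model has exponential PFS with medians of 11 and 17 months, a 30-month cap and very large simulated samples (300,000 patients; 150,000 for the last row). A fraction of controls is non-compliant, with the 11-month hazard multiplied as shown, and is withdrawn at a mean of 4 months. No PRRT patient is withdrawn. The comparison is the Cox HR with full follow-up against the HR after censoring at withdrawal. The full-follow-up HR differs from 0.647 because the subgroup's hazard is altered.

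| Controls non-compliant | Hazard multiplier | HR, full follow-up | HR, censored | Shift | Shift in log HR ÷ 0.158 |
|---|---|---|---|---|---|
| 5% | 1.5 | 0.635 | 0.644 | +0.009 | 0.09 |
| 10% | 2 | 0.614 | 0.637 | +0.023 | 0.23 |
| 15% | 3 | 0.578 | 0.617 | +0.039 | 0.41 |
| 10% | 0.5 | 0.695 | 0.655 | −0.040 | −0.38 |

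The last column is ln(censored/full)/0.158; in row two, ln(0.637/0.614)/0.158 = 0.037/0.158 = 0.23.

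**Outer bounds**

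These simulate 300 patients with 30 months of follow-up and a single-stage test, withdrawing 5, 10 or 15% of controls.

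- Withdrawal unrelated to outcome: HR stays at 0.645–0.647 and power at 87–88%, against 89% with none withdrawn. There is no bias.
- Every withdrawn control leaves 3 months before progression: HR 0.68, 0.72, 0.76; power 77%, 64%, 46%.
- Every withdrawn control would have been progression-free at month 30 and leaves in year 1: HR 0.58, 0.52, 0.46. Under a true HR of 1, false positives favouring 177Lu-edotreotide rise from 2.6% to 13.5%, 38% and 65%. The 15% case is a limit, since only about 100 × 2^(−30/11) = 15 of 100 controls would be progression-free then.

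The last two select patients on their future outcome. They bound the effect and do not predict it.

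**The case against.** Four stronger readings are tempting, and the documents support none of them.

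- **That 5.7 contradicts 4.4.1.** It does not, strictly. The 5.7 duty is to make every effort, and only during participation. What remains is a gap between the intent of 5.7 and a rule that can end the duty.
- **That a withdrawn patient has no further scan.** An exit MRI/CT is planned. It can capture progression already present, but not what follows.
- **That the rule targets controls.** The text is arm-neutral. Section 5.7 and Protocol 9.3.3.2 define compliance deviations for 177Lu-edotreotide as well, and missed visits and protocol deviations reach both arms. The defined everolimus deviation also excepts interruptions for toxicity, so poor tolerability alone does not meet it. The asymmetry is an inference about drug-taking, without rates.
- **That the rule favours the test drug.** In the worse-prognosis scenarios the HR moves toward 1, against 177Lu-edotreotide, by less than half a standard error.

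There are also mitigations. All randomised patients are analysed as randomised. Progression status is sought from drop-outs and non-compliant patients (Protocol 7.4.1), and the reason for each early termination is recorded (4.4.2). SAP 3.4.1 names local-read, alternative-censoring and drop-out-pattern analyses. These help only in part: the full analysis set still censors these patients, the later progression data are local, and the drop-out analysis is optional and has no stated method. The 15% dropout allowance replaces lost events but does not remove bias.

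**Conclusion.** The point holds as a cheap improvement to the design, with medium confidence. The protocol permits discretionary, unblinded removal from study follow-up for non-compliance or a deviation, and the primary analysis then censors the patient.

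The size and direction of any effect are unknown. Under the assumed worse-prognosis scenarios the shift is about 0.01 to 0.04 in HR, toward 1. With half the hazard in 10% of controls it is 0.04 the other way. These shifts rest on assumed fractions, hazards and withdrawal times, and on no such withdrawals in the PRRT arm. If withdrawal is unrelated to outcome, there is no bias. No stated sample-size figure changes.

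**What to change.** 1. In Protocol 4.4.1, 4.4.2 and 11.1.2, remove non-compliance and protocol deviation as reasons to end study participation. Whether study drug continues is a separate decision that this change leaves alone.
2. State that, unless consent is withdrawn, such patients stay in the study with RECIST imaging on schedule and blinded central reads until progression, death or month 30.
3. Report withdrawals from the study by arm and reason. The reasons are already collected, and SAP 6.1 and 6.6 already plan a flow diagram and treatment-discontinuation counts.
4. Turn the optional drop-out-pattern analysis in SAP 3.4.1 into a specified one. For example, count local progression after withdrawal as an event, and then treat withdrawals as events at the next scheduled scan, one arm at a time.

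The cost is protocol wording, a short SAP addition and some programming. The scans are already in the schedule. The downside is the burden of keeping non-compliant patients on them. Patients who simply stop attending will still be lost.

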#### 4.4.2 Withdrawal Procedures

Although patients are not obliged to give their reason(s) for withdrawing prematurely from a trial, the investigator should make every effort to ascertain the reason(s) for withdrawal while fully respecting the patient's rights. The investigator will make every effort to contact the patient and complete the EOS page on the case report form (CRF) and if possible the assessments outlined on EOS visit.

An EOS CRF page is to be completed for every patient, whether or not the patient completed the study. The reason for any early discontinuation should be indicated on this form. The primary reason for a patient withdrawing prematurely should be selected from the following standard categories of early termination:

- *Safety Reason/Adverse Event:* Clinical or laboratory events occurred that in the medical judgment of the investigator, for the best interest of the patient, are grounds for discontinuation. This includes serious and non-serious AEs regardless of relation to study medication. Criteria for dose-limiting toxicity are discussed in Section 5.4.3 and Table 9.
- *Protocol Violation:* The patient's findings or conduct failed to meet the protocol entry criteria or failed to adhere to the protocol requirements (e.g., drug non-compliance, failure to return for defined number of visits) as judged by the investigator or sponsor. The violation necessitated premature termination from the study.
- *Withdrawal of Consent:* The patient desired to withdraw from further participation in the study in the absence of an investigator-determined medical need to withdraw. If the patient gave a reason for withdrawing, it should be recorded.
- *Lost to Follow-Up:* The patient stopped coming for visits, and study personnel were unable to contact the patient (two unsuccessful phone contacts followed by registered letter and documentation in the source documents).

The date of study drug administration must be documented.

Appropriate follow-up of withdrawn patients will be performed, as required.

Attempts to contact a patient who withdraws from the study or is lost to follow-up must be documented.

Stopping rules for the entire study are described in Section 11.

#### 4.4.3 Replacement

Patients who drop out of the study before first treatment administration will be replaced. Additional enrolment will be performed for patients who have received study medication, but who do not have analysable efficacy data. As this is an open study, no specific replacement scheme is needed.

## **4.5 Patient Identification**

All patients who give informed consent will be identified by a unique identification number (“patient number”) that consists of 5 digits in two parts:

1. The site number is a 3-digit number that is provided by the sponsor prior to the start of recruitment.
2. The screening number is a 2-digit number that is consecutively assigned by the site to each patient after informed consent.

Example: The first patient screened by site “101” will receive patient number 101-01.

Example: The third patient at site “112” will receive patient number 112-03.

Investigational sites are required to keep a patient identification list, identifying their patients by name, date of birth, patient number and status (screen failure/completed study/withdrawn). This list will be reviewed by assigned monitors, but has to stay on site and will not be collected, in order to protect confidentiality.

## **4.6 End of the Study**

For regulatory purposes, the end of the study is defined as the last visit of the last patient or the last date of follow-up of toxicities, if required (whichever is later).

The end of study for each individual patient is the visit at month 30, unless disease progression, withdrawal from the study, or death occurs earlier.

## **4.7 Study Duration**

After providing informed consent, subjects will be screened for study enrolment, for up to 90 days prior to the first study treatment. Once enrolled and randomised to treatment, subjects will stay in the study until disease progression is established per RECIST 1.1 criteria, an alternative treatment for GEP-NET is initiated, the subject is withdrawn from the study, or for 30 months, whichever occurs first.

A subject randomised to everolimus (Afinitor®) who has disease progression must end study participation but may be offered Lu-edotreotide therapy based on the personal judgement of the Investigator, if he/she considers it appropriate and likely to be beneficial for the individual patient (see Section 7.4.2).

The maximum duration of participation for individual subjects is 30 months. The observation time for overall survival will be 5 years (60 months) after EOS for all patients (see Section 7.4).

## 5 Study Drug

### 5.1 Identity

#### 5.1.1 Chemical Properties of Lu-Edotreotide

The PRRT agent to be evaluated in the present study is Lu-edotreotide. Its chemical name is lutetium-177-Nα-[(4, 7, 10- triscarboxymethyl- 1, 4, 7, 10-tetraazacyclododec-1-yl)acetyl]-D-phenylalanyl-L-hemicystyl-L-tyrosyl-D-tryptophyl- L-Lysyl- L-threonyl- L-hemicystyl- L-threoninol cyclic (2→7) disulphide. Synonyms are:

[figure not shown]
- Lu-DOTATOC, (DOTA(0)-Phe(1)-Tyr(3)) octreotide, and
- Lu-DOTA-Tyr-octreotide.

Lu-edotreotide is radiolabelled with carrier-free lutetium-177 (Lu), a synthetic, low-energy beta and gamma emitting isotope of lutetium, the last element in the lanthanide series of metallic elements. Carrier-free Lu is generated by neutron irradiation of the isotope ytterbium-176 (Yb) and subsequent fractionation of Lu and Yb with cation chromatography. Key physical characteristics of Lu are summarised in [Table 5](#).

